17.7 Analysis of secondary endpoints

17.7.1 Equivalence in baseline-adjusted C_{max} and AUC_{0-inf}

 C_{max} and AUC_{0-inf} for each IP will be analysed for baseline-adjusted concentrations using the same model as described in Section 17.6.1.

Equivalence for each of the three NP products and at least one of the tobacco-based products will be concluded if the 90% CI for the ratio of C_{max} and AUC_{0-inf} , respectively, from the model falls within the acceptance interval of 80.00 - 125.00%.

17.7.2 In vivo extracted amount and fraction of nicotine

The difference between the nicotine content of an unused reference pouch and the used study pouch will be used to calculate the *in vivo* extracted amount and fraction of nicotine for each IP. Extracted amounts and fractions of nicotine will be presented using summary statistics. The amount of nicotine in the reference pouches will be presented through descriptive statistics.

Further details will be provided in the SAP.

17.7.3 Pharmacokinetics of nicotine in plasma

The following non-compartmental PK parameters will be determined for each IP: AUC_{0-inf} , AUC_{0-last} , $AUC_{0-1.5h}$, C_{max} , T_{max} , and $T_{1/2}$. Where possible, both baseline-adjusted and non-adjusted PK parameters will be calculated.

 C_{max} and T_{max} will be derived from the observed nicotine plasma concentration data. AUC_{0-1.5h}, AUC_{0-last}, and AUC_{0-inf} will be calculated using log-linear trapezoidal interpolation. Calculations will be based on the actual sampling times recorded during the study. Concentrations below the lower limit of quantification (LLOQ) occurring before C_{max} will be treated as zero. Concentrations below LLOQ occurring after C_{max} will be omitted from the analysis. All baseline-adjusted PK parameters will be corrected for nicotine plasma concentrations at baseline (pre-use).

 AUC_{0-inf} will be calculated as described in Section 17.4 above.

In addition, descriptive statistics for secondary PK parameters and concentrations (baselineadjusted and non-baseline-adjusted) will be presented. PK plasma concentration curves over time will be presented.

Further details will be provided in the SAP.

All data will be listed by subject number.

17.7.4 Pharmacodynamic effects

Oximeter pulse rates will be presented in descriptive summary tables and as mean plots over time for each IP.

The subjective parameters "craving", "satisfaction", "product-liking" and "intent to use again", measured by VAS, will be summarized for each IP using descriptive statistics during the IP use phase. Additionally, the relative and absolute change from baseline will be calculated for the subjective parameter "craving" for each IP and summarized.

To determine the maximum PD effect attributable to the IP, the highest increase from baseline (E_{imax}) , time to the first instance of E_{imax} (T_{Eimax}), the E_{max} from time 0 to 60 min ($E_{max0-60}$), and the time to reach $E_{max0-60}$ ($T_{Emax0-60}$) will be calculated for the pulse rates and presented using descriptive statistics.

For the subjective parameter "craving", the largest decrease from baseline (E_{dmax}) and time to E_{dmax} will be calculated and presented using descriptive statistics.

For the subjective parameter "satisfaction", which does not have a baseline, the highest value (E_{vmax}) and time to E_{vmax} will be calculated and presented using descriptive statistics.

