7.2 Secondary objective and endpoints

The secondary study objectives and endpoints are presented in Table 7.2-1.

Table 7.2-1Secondary objectives and endpoints

No.	Secondary objectives	No.	Endpoints	Assessments	Analysis
1.	To demonstrate equivalence in C_{max} and AUC_{0-inf} between each of the three NP products and at least one of the two tobacco-based products.	1.	Equivalence (90% CI for the ratio between 0.8 and 1.25) in baseline- adjusted C_{max} and AUC _{0-inf} based on nicotine plasma concentrations after administering single doses of the three NP products and the two tobacco- based products.	Nicotine plasma concentration analysis (Section 11.4.1)	See Section 17.7.1
2.	To compare the in vivo extracted amount (mg/unit) and extracted fraction (%) of nicotine from the three NP products with those from the two tobacco-based products.	2.	The difference in in vivo extracted amount (mg/unit) and extracted fraction (%) of nicotine between the three NP products and the two tobacco-based products.	Extracted amount of nicotine (Section 11.4.2)	See Section 17.7.2
3.	To compare the PK profile between the three NP products and the two tobacco-based products.	3.	The difference between the three NP products and the two tobacco-based products in the non-adjusted and baseline-adjusted PK parameters: AUC_{0-inf} , C_{max} , T_{max} , $AUC_{0-1.5h}$, AUC_{0-last} , and $T_{\frac{1}{2}}$.	PK blood sampling and analysis (Section 11.4.1)	See Section 17.7.3
4.	To assess the PD effects, measured as pulse rate and subjective outcome measures, of the three NP products and the two tobacco-based products.	4a.	PD (pulse rate): The difference between the three NP products and the two tobacco-based products for E_{imax} , T_{Eimax} , $E_{max0-60}$, and $T_{Emax0-60}$ in pulse rate, measured using a pulse oximeter after IP use.	Pulse rate evaluation (Section 11.4.3.1)	See Section 17.7.4
		4b.	PD parameters: The difference between the three NP products and the two tobacco-based products for E_{dmax} T_{Edmax} in the subjective parameter	Subjective outcome evaluation (Section 11.4.3.2)	See Section 17.7.4

			"craving", measured using a 100 mm VAS after IP use.		
		4c.	PD parameters: The difference between the three NP products and the two tobacco-based products for E_{vmax} and T_{Evmax} in the subjective parameter "satisfaction", measured using a 100 mm VAS after IP use.	Subjective outcome evaluation (Section 11.4.3.2)	See Section 17.7.4

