	4d.		PD (subjective outcome parameters): The difference between the three NP products and the two tobacco-based products for the subjective parameters "product-liking" and "intent to use again", measured using a 100 mm VAS 30 min after IP use.	Subjective outcome evaluation (Section 11.4.3.2)	See Section 17.7.4
5.	To evaluate the safety and tolerability of the three NP products and the two tobacco-based products by administering single doses in current, daily oral tobacco/NP users.	5.	Frequency, intensity, and seriousness of AEs.	AE reporting (Section 11.4.4)	See Section 17.7.5

AE=adverse event, AUC=area under the plasma concentration vs. time curve, AUC_{0-inf} = AUC from 0 to infinity, AUC_{0-last} = AUC from 0 to time of last measurable plasma concentration, $AUC_{0-1.5h}$ = AUC from time 0 to time 1.5 hours, CI=confidence interval, C_{max} =maximum observed concentration, E_{dmax} =largest decrease from baseline, E_{imax} =highest increase from baseline, E_{vmax} = largest value, IP=investigational product, NP=nicotine pouch, PD=pharmacodynamic, PK=pharmacokinetic, T_{Edmax} =time to the first instance of E_{dmax} , T_{Eimax} = time to the first instance of C_{max} , T_{Evmax} = time to the first instance of E_{vmax} , VAS=visual analog scale

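### Secondary endpoints 4a–4d are defined as nicotine pouch versus snus differences, but Section 17.7.4 plans only per-product descriptive statistics, so those differences are not estimated

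*Protocol*

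**What the plan says.** In protocol Table 7.2-1 (Section 7.2), endpoint 4a opens "PD (pulse rate): The difference between the three NP products and the two tobacco-based products for" four pulse-rate parameters. Endpoints 4b (craving) and 4c (satisfaction) follow the same pattern. Endpoint 4d is "The difference between the three NP products and the two tobacco-based products for the subjective parameters" product-liking and intent to use again. The analysis column refers all four to Section 17.7.4.

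Section 17.7.4 says that the pulse-rate parameters "will be calculated for the pulse rates and presented using descriptive statistics" and that the four VAS ratings "will be summarized for each IP using descriptive statistics during the IP use phase". Craving also gets absolute and relative change from baseline for each product. The craving and satisfaction extremes, and the times to reach them, are likewise reported descriptively.

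Elsewhere the protocol does state contrasts. Sections 17.6.1 and 17.7.1 fit a mixed model to log-transformed Cmax and AUC0-inf and report ratios of geometric least square means with 90% confidence intervals. Section 8.2 justifies the crossover on the ground that subjects act as their own controls.

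**The concern.** An endpoint defined as a difference needs an analysis that yields a difference and a measure of its precision. Section 17.7.4 yields five separate columns of means, SDs and quantiles. These show how each product behaved. They do not say how far an NP product lies from a snus product, or how well that distance is known. Marginal SDs do not carry the within-subject correlation, so an interval for the paired difference cannot be derived from the summary tables.

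Section 6.1 presents PK/PD studies as central to judging the abuse liability of pouches against snus. Craving relief, satisfaction, liking and intent to use again are the subjective side of that judgement. Under the stated analysis, any sentence in the report calling an NP product lower than, or close to, a snus product on these measures would rest on comparing marginal summaries by eye.

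**Working it through.** The protocol gives no sample size, power or precision figure for endpoint 4, so there is no stated number to reproduce. The check sets each definition beside its analysis.

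**Endpoint 4 (Table 7.2-1 against Section 17.7.4)**

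| Endpoint | Parameters | Count | Defined as | Stated analysis |
|---|---|---|---|---|
| 4a pulse rate | Eimax, TEimax, Emax0-60, TEmax0-60 | 4 | NP–tobacco difference | descriptive |
| 4b craving | Edmax, TEdmax | 2 | NP–tobacco difference | descriptive |
| 4c satisfaction | Evmax, TEvmax | 2 | NP–tobacco difference | descriptive |
| 4d VAS at 30 min | product-liking, intent to use again | 2 | NP–tobacco difference | descriptive, per product |

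Total: 4 + 2 + 2 + 2 = 10 parameters, of which 0 have a stated between-product contrast. The change from baseline given for craving is a change within a product visit, not a difference between products.

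**Is the contrast supplied elsewhere?** Section 17.1 says that formal comparisons go to a designated reference product, but names neither the reference nor the endpoints. Sections 17.6.1 and 17.7.1 cover Cmax and AUC0-inf only. Section 17.8.2 covers extraction and extraction-normalized PK only. None reaches endpoint 4.

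**Neighbouring endpoints, to fix the boundary of the point**

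- Endpoint 3 is "The difference between the three NP products and the two tobacco-based products in the non-adjusted and baseline-adjusted PK parameters": 6 parameters × 2 versions = 12 quantities. Baseline-adjusted Cmax and AUC0-inf (2 of 12) get a modelled ratio with a 90% interval. For the other 10, Section 17.7.3 mentions "descriptive statistics for secondary PK parameters and concentrations" and leaves further detail to the SAP.
- Endpoint 2 is the difference in "extracted amount (mg/unit) and extracted fraction (%) of nicotine between the three NP products and the two tobacco-based products". Section 17.7.2 says "Extracted amounts and fractions of nicotine will be presented using summary statistics" and also defers to the SAP. Section 17.8.2 announces a comparison of extracted amount and fraction without naming a method.

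**What the design could deliver for endpoint 4.** With 38 evaluable subjects, complete data over 5 periods, and the Section 17.6.1 model (product fixed, subject random), the residual degrees of freedom are (38 − 1) × (5 − 1) = 148. The 90% half-width for a product difference, in units of the residual within-subject SD, is t(0.95; 148) × √(2/38) = 1.655 × 0.2294 ≈ 0.38. That precision is available from data already to be collected.

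**Number of intervals.** 3 NP × 2 tobacco products = 6 contrasts per parameter. Six continuous parameters give 6 × 6 = 36 and four time parameters give 4 × 6 = 24, so 60 in all.

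**The case against.** The best defence has four parts.

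- *The SAP may supply the contrasts.* Section 17 says that it gives principal features and that the SAP elaborates them. This is decisive for endpoints 2 and 3, whose sections defer to the SAP. It is weaker for endpoint 4: Section 17.7.4 does not leave the matter open but states a descriptive analysis, which does not produce the quantity defined in Table 7.2-1. That conflict lies within the protocol.
- *Objective 4 is to assess, not to compare.* This is true, and descriptive summaries suit that verb. The endpoint column still says difference four times, so one of the two must change.
- *The pairing is not lost.* Section 17.1 provides listings by subject and product, from which paired differences could be computed. That stands, but a reader's own calculation from listings is not a prespecified estimate.
- *The study's goal is matching on Cmax (Section 6.2), and that contrast is modelled.* This also stands and limits the consequence.

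A reader might infer that no difference or precision is estimated for any of endpoints 2–4. The documents do not support this: two endpoint 3 quantities have modelled ratios with intervals, a comparison of extraction is announced, and the remaining detail is deferred to an SAP that is not at hand. A reader might also want to put a figure on the precision lost by treating the product means as independent. No within-subject correlation is given and no such unpaired calculation is planned, so that figure would describe an analysis that nobody proposes.

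**Conclusion.** The point holds for endpoints 4a–4d: 10 of 10 pharmacodynamic parameters are defined as NP–tobacco differences and none has a stated estimate of that difference. The same gap may exist for the 10 remaining endpoint 3 quantities and for the method of the extraction comparison, but no error is asserted there because those sections defer to the SAP.

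The consequence is moderate. The primary endpoint and the equivalence analyses are unaffected, and descriptive reporting of pharmacodynamic data would be defensible had the endpoints been worded that way. The conclusion rests on the protocol text alone and on no assumed correlation. The half-width of about 0.38 within-subject SD assumes 38 complete subjects and a common residual variance; it shows only what the design could offer.

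**What to change.** In Section 17.7.4, add that:

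- Eimax, Emax0-60, Edmax, Evmax, product-liking and intent to use again are each analysed on the untransformed scale with the crossover mixed model of Section 17.6.1, reporting the six NP-minus-tobacco differences with confidence intervals;
- TEimax, TEmax0-60, TEdmax and TEvmax are compared by paired within-subject differences, for example Hodges–Lehmann estimates with confidence intervals;
- all of these are non-confirmatory and unadjusted for multiplicity.

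State the confidence level; 90% would match Section 17.6.1. Keep the descriptive tables. The SAP is to be signed before database lock, so the contrasts can still be prespecified up to then.

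The cost is protocol and SAP wording, six model fits, four sets of paired estimates and up to 60 unadjusted intervals, which is why the non-confirmatory label matters. If the sponsor wants description only, rewording endpoints 4a–4d as per-product summaries would remove the contradiction, but the trial would then give no estimate of the pharmacodynamic differences.

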17.7.5 Adverse events

An overview of all AEs, including SAEs, intensity, and deaths will be presented by IP. The incidence of AEs and SAEs will be summarized by SOC and PT for each IP.

All AE data will be listed by subject number and include the verbatim term entered by the Investigator.

17.8 Analysis of exploratory objectives

17.8.1 Exploratory subjective parameter

The subjective parameter "product-liking" *vs*. the subjects' usual snus/nicotine product of choice, measured through MCQ, will be summarized for each IP using descriptive statistics in a frequency table.

17.8.2 Extraction normalized AUC_{0-inf} and C_{max}

Nicotine extraction normalized PK parameters AUC_{0-inf} and C_{max} (both with and without baseline adjustment, divided by the extracted amount), will be determined for the three NP products (all 3 mg, moist and dry) and the two tobacco-based products (4 mg and 8 mg). The analysis will compare the differences in AUC_{0-inf} , C_{max} , and the extracted amount and fraction of nicotine between the NP products and the tobacco-based products.

Additionally, extraction normalized AUC $_{0-inf}$ and C_{max} data will be presented for each IP using summary statistics.

